## 6.2.6. Length of Initial Hospital Stay

The number and percentage of subjects who were hospitalized at the time they were screened for the study will be presented by treatment group. The denominator for percentage will be the number of subjects in the FAS or modified ITT analysis set (as appropriate).

For those hospitalized at the time they were screened for the study, the following will be presented (denominator for percentage will be number hospitalized in appropriate analysis set):

- Number and percentage of subjects who were transferred from another hospital to the current hospital where they are participating in this study
- Number of subjects who were released from the hospital after the screening visit and prior to first dose of SEL/PLA study drug
- Number and percentage of subjects still in the hospital on Study Day 1.

In addition, for those still in the hospital on Study Day 1, summary statistics of days hospitalized from date of first dose of SEL/PLA by treatment group and death status (eg., alive or dead) will be presented where

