# 3. GENERAL CONSIDERATIONS FOR DATA ANALYSES

Analysis results will be presented using descriptive statistics. For categorical variables, the number and percentage of subjects in each category will be presented; for continuous variables, the number of subjects (n), mean, standard deviation (SD), median, first quartile (Q1), third quartile (Q3), minimum, and maximum will be presented.

All statistical tests (PPD ) will be 2-sided and performed at the 5% significance level unless otherwise specified.

By-subject listings will be presented for all subjects in the Safety Analysis Set unless otherwise specified. Listings will be sorted by subject ID number, visit date, and time (if applicable). Data collected on log forms, such as AEs, will be presented in chronological order within the subject. The treatment group to which subjects were randomized will be used in the listings. Age, sex at birth, race, and ethnicity will be included in the listings, as space permits.

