## 6.1. Secondary Efficacy Endpoints:

- Number (%) of subjects who die by Study Day 28 and by Weeks 8, 12, and 24
- Number (%) of subjects receiving a liver transplant by Study Day 28 and by Weeks 8, 12, and 24
- Summary of Lille score by visit through Week 4
- Number (%) of subjects with Lille response (score < 0.45) at Day 7 (eg, Week 1)
- Number (%) of subjects with Lille null response (score  $\ge 0.56$ ) at Day 7 (eg, Week 1)
- Mortality Risk at Months 2 and 6 based on Lille score response at Day 7 (eg, Week 1) and the baseline MELD score (continuous)
- Number (%) of subjects with infection while on study
- Number (%) of subjects with HRS while on study
- Length of initial hospital stay
- Change from baseline in liver biochemistry tests (ALT, AST, GGT, albumin, alkaline phosphatase, total bilirubin, direct bilirubin, and INR) by analysis visit through Week 24
- Change from baseline in prognostic indices (MELD, CPT, and Maddrey's DF) by analysis visit through Week 24

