#### 6.2. Analysis Methods for Secondary Efficacy Endpoints

#### 6.2.1. Death

The number (%) of subjects with a death by Study Day 28, and by Weeks 8, 12, and 24 will be displayed by treatment group. For the endpoint death by Day 28, subjects who die on/prior to Study Day 28 or are known to be alive through Study Day 28 will be included in the denominator for calculation of percentage of subjects with death. Subjects not followed through Day 28 will be summarized by their reason for premature discontinuation from study. A 2-sided

Fisher's exact test will be used to explore whether there are differences between treatment groups in percentage of subjects with death by Day 28. Deaths by Weeks 8, 12, and 24 will be summarized in the same manner as deaths by Study Day 28. Kaplan-Meier estimates of survival and the 95% CI (based on Greenwood's formula and the log-log transformation of the survival function) will also be presented at each timepoint. A Kaplan-Meier figure for survival will be displayed. Deaths will be recorded on the Death and/or survival status eCRF and the date of last subject follow-up will be determined from the maximum of eCRF visit dates (including subject survival status visit dates), and Covance laboratory collection dates.

A listing of subject deaths while on study will be provided for the mITT analysis set; subjects included in the FAS will be flagged. Days from first dose of study drug (ie, Study Day) and days from last dose of study drug (ie, Follow-up Day) for subjects for whom death occurs after stopping study drug, will be provided in the listing.

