## Days hospitalized from first dose of SEL/PLA =

(Date of release from hospital – date of first dose of SEL/PLA +1)

If the death date is the same as the release date or the subject has a nonmissing death date and there is no release date from hospitalization, the subject will be assumed to be "dead" upon release from the hospital. Date of death will be substituted for date of release in the formula for days hospitalized from first dose of SEL/PLA.

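### Length of initial hospital stay is summarised by arm only within alive and dead strata, so between-arm differences are not treatment effects and may be biased in either direction

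*SAP*

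**What the plan says.** Protocol 8.2 and SAP 6.1 list this endpoint among the secondary outcomes; the SAP wording is "Length of initial hospital stay". SAP 6.2.6 first counts who was hospitalised at screening, transferred, released before dosing or still an inpatient at first dose. The duration is then summarised "for those still in the hospital on Study Day 1", as "summary statistics of days hospitalized from date of first dose of SEL/PLA by treatment group and death status".

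The duration is release date minus first-dose date plus 1. A subject counts as dead at release if the death and release dates coincide, or if there is a death date and no release date. For these subjects, "Date of death will be substituted for date of release in the formula for days hospitalized from first dose of SEL/PLA".

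Tables 15.9.2.5.1 (Full Analysis Set, FAS) and 15.9.2.5.2 (modified ITT) carry the result. Section 6.2.6 names no test, interval or model. It also describes no summary across both strata, no competing-event analysis and no fixed-horizon composite. SAP 3 sets the general rule: "Analysis results will be presented using descriptive statistics". Deaths are handled elsewhere, in SAP 6.2.1: "The number (%) of subjects with a death by Study Day 28, and by Weeks 8, 12, and 24 will be displayed by treatment group".

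**The concern.** Randomisation makes the two arms comparable as a whole. It does not make the subjects discharged alive in one arm comparable with those discharged alive in the other, because treatment may affect who gets into that group. The same holds for the dead stratum. If the drug changed in-hospital mortality, the survivors in the two arms would be differently selected, and their mean stays could differ with no effect on time to discharge.

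The dead row has a second problem, which needs no assumption about selection. The quantity shown there is time from first dose to death, under a label that reads as length of stay. A shorter value is usually taken as good; here it means faster death.

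Death is common enough in this population to matter. Protocol 1.1 cites 1-month mortality of about 20% with prednisolone and about 35% without treatment. As planned, the table gives no between-arm contrast that answers the secondary objective on hospital stay.

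**Working it through.** The plan states no figure for this endpoint, so there is nothing to reproduce. The check asks what the planned table would show if treatment had **no** effect on time to live discharge and only mortality differed.

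**Inputs**
- Scale of stay: Protocol 1.1 gives a mean of 5 to 7 days. Assumed: time to live discharge L = 6 × exp(0.7 × U), with U standard normal (median 6 days, log-SD 0.7), identical in every arm.
- In-hospital mortality: not given in the documents. Assumed 10%, 20% and 35%, a range set by the 1-month figures in Protocol 1.1.
- Who dies: either independent of L, or with probability 1/(1 + exp(−(m + bU))), where m is tuned to the target mortality. b = +1.5 puts deaths mainly in would-be long stayers; b = −1 puts them mainly in would-be short stayers.
- When: early death is L × V and late death is L × (1 + V), with V uniform on 0 to 1. Stay ends at death, as in the SAP.
- 400,000 simulated subjects per arm.

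**Mean days**

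| Scenario | Row | 10% die | 20% die | 35% die |
|---|---|---|---|---|
| A. Death unrelated to L, early | alive | 7.65 | 7.68 | 7.68 |
| | dead | 3.82 | 3.83 | 3.84 |
| | pooled | 7.26 | 6.91 | 6.34 |
| B. Long stayers die, early | alive | 6.82 | 6.21 | 5.52 |
| | dead | 7.69 | 6.71 | 5.80 |
| C. Short stayers die, early | alive | 8.05 | 8.45 | 9.09 |
| | dead | 2.09 | 2.29 | 2.52 |
| D. Long stayers die, late | alive | 6.79 | 6.20 | 5.51 |
| | pooled | 8.44 | 9.00 | 9.69 |

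**Hand check of A.** The mean of L is 6 × exp(0.7²/2) = 7.67. Early deaths average half of that, 3.83. Pooled at 20% mortality: 0.8 × 7.67 + 0.2 × 3.83 = 6.90, against 6.91 simulated.

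**Reading, 10% against 20% mortality, alive row**
- A: no change beyond simulation noise.
- B: 6.21 − 6.82 = −0.61 days; the higher-mortality arm looks shorter.
- C: 8.45 − 8.05 = +0.40 days; it looks longer.

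**Dead row at equal mortality.** With 20% mortality in both arms and deaths twice as early in one, the dead-row means are 3.83 and 1.92 days. The arm whose subjects die sooner shows half the stay.

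**Size against sampling noise.** Suppose 50 FAS subjects per arm, all in hospital on Day 1. With 10% and 20% deaths, 45 and 40 are discharged alive. Taking the SD of L, 7.67 × √(exp(0.49) − 1) ≈ 6.10 days, the standard error of the difference is about 6.10 × √(1/45 + 1/40) ≈ 1.3 days. The 0.61-day shift in B is roughly half of one standard error (0.61/1.3 ≈ 0.47).

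**The case against.** The strongest reply is that the split is a sensible choice. A pooled mean would mix truncated stays with completed ones, and scenario A shows the pooled mean shortening as deaths rise (7.26, 6.91, 6.34) while the alive row stays flat. Separating the dead keeps those truncated stays out of the discharged-alive figure. That stands: the split is better than naive pooling.

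A reader might infer that the table makes the arm with more deaths look as if it has shorter stays, and so would present harm as benefit. The documents do not support that direction. It needs deaths to fall mainly on would-be long stayers. Protocol 1.1 makes this plausible, with about 45% 90-day mortality in infected patients against about 5% in uninfected ones, and Protocol 6.9.9 sets minimum antibiotic courses of 5 to 14 days by infection type. Neither passage links death to would-be stay, and Protocol 4.3 excludes the most severe cases (MELD above 30, Maddrey's DF above 60, Grade 4 encephalopathy). Scenario C reverses the sign.

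It is also true that no formal comparison is planned. The SAP's general rule that tests "will be 2-sided and performed at the 5% significance level unless otherwise specified" is not applied here, whereas Fisher's exact test is specified for death and for Lille response. The summary statistics include n, so the table itself shows how many subjects fall in each row. Deaths, survival curves and transplant-free survival are all reported by arm. These safeguards limit the harm, but they leave the reader to combine separate tables informally, and none gives an interpretable arm contrast for hospital stay.

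**Conclusion.** The point holds as a limited one. The only planned summary of post-dose stay is stratified by an outcome that arises after randomisation, so within-stratum arm differences do not estimate a treatment effect and may err in either direction. In the dead stratum, earlier death reads as a shorter stay, whoever dies.

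In the illustration, a 10-point difference in mortality shifts the alive-row mean by between −0.61 and +0.40 days with no true effect on discharge. Those figures rest wholly on the assumed stay distribution, mortality levels and link between death and stay; they show that the sign is undetermined and do not predict this trial's bias. The shift is small beside sampling error at this sample size.

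The consequence is minor: one descriptive secondary endpoint in a phase 2 study whose primary endpoint is safety, with mortality reported separately by arm.

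**What to change.** For all FAS subjects in hospital on Study Day 1, add one of the following by arm:
- **Days alive and out of the initial hospitalisation through Day 28**, with no further days credited after death. Release on Day 7 and alive at Day 28 scores 28 − 7 = 21; death in hospital on Day 7 scores 0. The current formula gives both subjects 7 days, in different rows.
- **Cumulative incidence of live discharge**, with in-hospital death as a competing event. This keeps discharge and death visible as separate outcomes, whereas the first option combines them and will partly restate mortality.

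Keep the split table as supportive, with a footnote that arm differences within a stratum are not treatment effects.

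The cost is one extra output to produce and explain. Release and death dates are already used in SAP 6.2.6, and Protocol 6.3.4 provides a phone contact between Days 28 and 35 to establish survival when the Week 4 visit falls before Day 28, so no new data are needed. The real downside is timing. SAP 2.3 shows that treatment was unblinded for the primary analysis before this plan for the final analysis, and SAP 6.5 already records that no efficacy improvement was seen. The new table must therefore be labelled as specified after unblinding. If the SAP is already final, SAP 1 requires the change to be documented in the clinical study report.

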## Days hospitalized from first dose of SEL/PLA =

(Date of release from hospital – date of first dose of SEL/PLA +1)

If the death date is the same as the release date or the subject has a nonmissing death date and there is no release date from hospitalization, the subject will be assumed to be "dead" upon release from the hospital. Date of death will be substituted for date of release in the formula for days hospitalized from first dose of SEL/PLA.

#### 6.2.7. Events of Interest

The number and percentage of subjects with the following 2 types of events will be summarized:

- Infections of Interest (as described in Section 6.9.9 of the study protocol)
- Hepatorenal Syndrome events (meeting International Ascites Club criteria as described in Section 6.9.8 of the study protocol)

A postbaseline infection of interest will be considered to be "definite" in subjects with clinical evidence of infection (ie, AE with the infection field marked 'yes' on the AE eCRF) and a positive culture from a normally sterile source; infiltrate on chest x-ray and treatment with antibiotics; or ascitic fluid neutrophils  $\geq 250$  cells/mm^3, regardless of culture positivity for SBP. All other infections will be considered to be "probable". Results from laboratory investigations

will be used to enter the most specific AE verbatim term possible for coding purposes (ie, "*E. Coli* urinary tract infection" for a urinary tract infection where the pathogen "*E. Coli*" was present in a urine culture); and to serve as source documentation of the methods used to determine that the infection was "definite".

A summary of postbaseline "infections" (ie, adverse events that have 'yes' marked for infection on the AE eCRF) will be presented by treatment group, high level group term (HLGT) and lower lever term (LLT) from the MedDRA dictionary separately for infections that are "definite" infections and for those that are "definite/probable" infections. Multiple events reported within a HLGT, and LLT will be counted once only per subject in each summary. Infections will be summarized in alphabetic order of HLGT and then by LLT in descending total frequency within each HLGT. Infections with postbaseline onset dates or worsening on or after the first dose date of study drug through end of study will be summarized.

Culture and x-ray results collected for documenting definite infections will be presented alongside the reported infection in a listing sorted by start date for the infection and procedure date for the culture/x-ray. Cultures collected on/after Study Day 1 will be listed.

Postbaseline medications used to treat infections (identified from an indication of "Infection" on the CM eCRF) will be summarized by treatment group and preferred name. Medications with stop dates prior to first dose date of SEL/PLA will be excluded.

A listing of subjects with HRS events entered on the AE eCRF that meet International Ascites Club criteria as described in Section 6.9.8 of the study protocol will be provided. Subjects with an AE preferred term of "Hepatorenal syndrome" from the AE eCRF will be screened by the medical monitor to determine whether the event meets Ascites Club HRS criteria. New or worsening postbaseline HRS events reported during the study will be summarized.

Medications used to treat HRS (ie, those with an indication of 'HRS' on the concomitant medication eCRF) will be summarized by treatment group and preferred name. Medications with stop dates prior to first dose date SEL/PLA will be excluded from analyses. Medications used to treat HRS will be listed.

## 6.2.8. Liver Biochemistry and Prognostic Indices

Summary statistics for the absolute value and change and percentage change from baseline for liver biochemistry tests (ALT, AST, GGT, albumin, alkaline phosphatase, total bilirubin, direct bilirubin, and INR) and prognostic indices (MELD, CPT and Maddrey's DF) will be presented by visit through Week 24 using central laboratory data except when noted otherwise (see Section 3.8.2 of the SAP for visit windows; and Section 3.6.1 for baseline MELD imputation rule when central laboratory data is not available).

Percentage change from baseline is calculated as:

([score at visit – score at baseline]  $\div$  score at baseline)  $\times$  100

An additional timepoint will be added for "Week 4 (LOCF)". For this additional timepoint, a subject will be included with their Week 4 value, or with the last chronologic value collected between Study Days 2 and 24 for subjects who are missing a Week 4 value. For all liver biochemistry tests and prognostic scores, subjects who receive a liver transplant while on study will have measurements collected up to the date of transplant included for summary tables.

Median (Q1, Q3) absolute values by visit will be plotted for MELD score, ALT, AST, total bilirubin and INR throughWeek 24 for the final analysis. Median (Q1, Q3) change and percentage change from baseline by visit will be plotted for MELD score and for total bilirubin.

A listing of values included in efficacy analyses will be provided with subjects included in the FAS flagged in listings.

Formulas for calculating each of the prognostic indices are described below:

*Maddrey DF score* = [4.6 × (PT subject [sec] – PT control [sec])] + total bilirubin (mg/dL)

Note: PT control [sec] is only available at the screening visit for each subject. For calculations over time, the subject's screening PT control [sec] will be used to calculate scores at each of the visits.

 $MELD \ score = 10 \times \{[0.957 \times Ln(Scr)] + [0.378 \times Ln(Tbil]) + [1.12 \times Ln(INR)] + 0.643)\},\$ 

where Scr = serum creatinine (in mg/dL), Tbil = Total Bilirubin (in mg/dL), INR = international normalized ratio, and Ln = natural log. If any lab value is less than 1.0, then it will be set to 1.0 in the calculation. If the subject received dialysis at least twice in the past week, or if serum creatinine is > 4.0 mg/dL, then Scr will be set to 4.0 mg/dL in the above formula. The result will be rounded to the nearest whole number. Subjects missing a baseline MELD score using central laboratory data will have their baseline MELD score imputed as described in Section 3.6.1 of this SAP.

*CPT score* = Sum of the scores related to the 5 parameters below for a given subject and study visit (if any of the components are missing, the score will not be calculated for that subject and visit):

	POINTS			
Parameter	1	2	3	
Encephalopathy	None	Grade 1-2 (medication controlled)	Grade 3-4 (medication refractory)	
Ascites	None	Mild/Moderate (diuretic responsive)	Severe (diuretic refractory)	
Bilirubin (mg/dL)	< 2	2 - 3	> 3	
Albumin (g/dL)	> 3.5	2.8 - 3.5	< 2.8	
INR	< 1.7	1.7 - 2.3	> 2.3	

Note: if either ascites or encephalopathy is "none" because the subject is taking medication which has controlled the symptoms, the scoring should be 2 points (not 1 point).

The CPT score is obtained by adding the points for each parameter for a given subject at a visit. The CPT class is assigned based on the score: CPT A (5-6 points), CPT B (7-9 points), CPT C (10-15 points).

For the MELD and CPT calculations, the dates for each of the individual laboratory tests utilized in the formula are collected on the CPC\_MELD eCRF and merged with the Covance laboratory dataset by laboratory test and laboratory collection date prior to calculating the scores. The visit date for the CPC\_MELD eCRF determines the study day for purposes of determining the analysis visit windows as specified in Section 3.8.2 of this SAP.

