1. INTRODUCTION

1.1. Background

Alcoholic liver disease (ALD) encompasses a spectrum of disease ranging from reversible fatty liver to alcoholic hepatitis (AH) and cirrhosis. In the United States, ALD remains the second most common cause of liver cirrhosis after Hepatitis C virus (HCV) infection and is responsible for approximately 20% to 25% cases of liver cirrhosis {Gao 2011, Singal 2013}. In Western Europe, ALD is the most prevalent cause of advanced liver disease and cirrhosis is the leading cause of alcohol-related death among adults {European Association for the Study of the Liver (EASL) 2012}.

AH represents one of the most serious forms of ALD and remains a significant cause of morbidity and mortality in North America and Europe. Approximately 60% of patients with ALD in the United Kingdom will have evidence of an alcohol-related hepatitis at presentation {Hislop 1983}. In the United States (US), the burden of AH is increasing, with an estimated 326,000 hospitalizations (0.8% of all admissions) in 2010, a 30% increase compared with 2002 {Jinjuvadia 2015}. The mean length of a hospital stay is 5 to 7 days with an average health care cost of \$35,000 to \$41,000. In patients with severe AH (typically defined by a Maddrey's Discriminant Function (DF) \geq 32, short-term mortality rates are high (approximately 25% to 45%) {Akriviadis 2000, Mathurin 2011}.

AH is a syndrome characterized by infiltration of the liver by inflammatory cells and hepatocellular injury. Several studies in rodent models and histopathological studies in humans suggest that lipopolysaccharide (LPS)-induced inflammation and oxidative stress are key drivers of hepatocyte death in AH {Chayanupatkul 2014, Lucey 2009, Meagher 1999}. Alcohol consumption increases intestinal permeability and bacterial translocation to the liver, resulting in LPS-induced hepatic inflammation. Subsequent hepatocellular injury occurs by neutrophil oxidative bursts, and FAS ligand and TNF- α induced hepatocyte apoptosis. In addition, ethanol strongly induces the expression of CYP2E1, which produces reactive oxygen species (ROS) as a by-product of ethanol metabolism, and reduces hepatic antioxidant capacity. Oxidative stress occurs as a result of these changes and directly induces hepatocyte mitochondrial dysfunction and necrosis and also sensitizes hepatocytes to apoptosis induced by TNF- α and FAS ligand {Cederbaum 2012}.

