#### 3.5. Multiple Comparisons

# 3.6. Missing Data and Outliers

#### 3.6.1. Missing Data

In general, missing data will not be imputed unless methods for handling missing data are specified, except for the cases described below.

For subjects who are missing a baseline central laboratory-calculated MELD score, the subject's screening local laboratory-calculated MELD score used to assess inclusion and exclusion criteria and to stratify the subject for randomization will be used in place of the missing central laboratory-calculated baseline MELD score.

For Lille scores, if the Week 1 Lille score for an individual subject cannot be calculated using central laboratory data and a Week 1 Lille score using local laboratory data is available, then Lille scores for that subject will be calculated using local laboratory data for all Lille score timepoints (eg, at Weeks 1, 2, 3, and 4). If both central and local laboratory Week 1 Lille scores are not calculable, then central laboratory data will be used to calculate Lille scores for all visits.

Individual subjects for whom the above imputation rules will be applied will be outlined in the Programming and Analysis Specifications (Appendix 2 of this SAP), along with the reason for their imputation.

For subjects missing a last dose date of study drug, imputation rules are described in Section 4.2.1. The handling of missing or incomplete dates for AE onset is described in Section 7.1.5.2, and for missing start dates for prior and concomitant medications in Section 7.4.

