# 6. EFFICACY ANALYSES

The primary efficacy analysis will include subjects in the FAS. A secondary analysis of efficacy will include subjects in the mITT analysis set. Subjects who receive a liver transplantation while enrolled in the study will have measurements collected up to the time of liver transplantation included in efficacy analyses; data collected after transplantation will be excluded from efficacy analyses.

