Lille score will additionally be summarized as a categorical variable at Week 1, Week 2, and at Week 4 (LOCF) by treatment group and visit for the following:

- 1) The number and percentage of subjects with a Lille response, defined as a Lille score < 0.45 (yes or no)
- 2) The number and percentage of subjects with a Lille null response, defined as a Lille score  $\geq 0.56$ , will be displayed by treatment group and visit. Null response is used as a criteria for premature discontinuation of prednisolone in clinical practice. Subjects with a complete or partial response (Lille score < 0.56) will be further subdivided into complete responders (Lille score < 0.16) and partial responders (Lille score 0.16 to < 0.56).

The denominator for the percentage calculation will be the number of subjects in the treatment group for the FAS or mITT analysis set (as appropriate). Subjects missing a Lille score value within the visit window will be counted as failures. Subjects with a calculated Lille score meeting non-responder or null-responder criteria will be summarized as "observed" failures. Subjects missing a value within the visit window will be summarized as "missing value". The reasons for subjects not having a Lille score will be summarized at each visit as follows:

- 1) Subjects who discontinue both study drugs in the regimen prior to the target day (ie, Study Days 7 [Week 1 and Week 4 LOCF] and Day 14 [Week 2] for the visit window will be summarized by the premature discontinuation reason for SEL/PLA from the study drug completion eCRF.
- 2) Subjects ongoing at the time of the visit will be summarize as "missing value at visit"

For the endpoints Lille response (yes, no) and Lille null response (vs. complete or partial response), p-values from a 2-sided Fisher's exact test will be presented for the Week 1 visit to explore whether there are differences between treatment groups.

A listing of the Lille scores included in analysis will be provided. A footnote will provide Subject IDs for those subjects who had Lille scores calculated using local laboratory data.

#### 6.2.5. Mortality Risk using Baseline MELD score and Lille Score at Day 7

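### By-visit MELD, bilirubin, CPT and Maddrey DF summaries cover only subjects alive, untransplanted and sampled, so unequal mortality can tilt them towards the arm with more deaths

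*SAP*

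**What the plan says.** SAP 6.1 lists among the secondary efficacy endpoints "Change from baseline in prognostic indices (MELD, CPT, and Maddrey's DF) by analysis visit through Week 24", and treats the liver biochemistry tests, including bilirubin, the same way. SAP 6.2.8 says that absolute value, change and percentage change "will be presented by visit through Week 24 using central laboratory data except when noted otherwise". It plans median (Q1, Q3) plots of absolute value, change and percentage change for MELD and total bilirubin.

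The default in SAP 3.6.1 is: "In general, missing data will not be imputed unless methods for handling missing data are specified, except for the cases described below". The cases listed there are baseline MELD, Lille scores from local laboratory data, and dates. None concerns death. For transplant, SAP 6 says that "data collected after transplantation will be excluded from efficacy analyses".

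SAP 6.2.8 also adds a Week 4 (LOCF) time point: "a subject will be included with their Week 4 value, or with the last chronologic value collected between Study Days 2 and 24". It makes no exception for subjects who died.

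Other parts of the SAP do deal with death or missing values. For the categorical Lille outcomes in SAP 6.2.4, "Subjects missing a Lille score value within the visit window will be counted as failures". SAP 6.2.6 splits hospital stay by whether the subject was alive or dead. SAP 6.2.1 and 6.2.3 report death and transplant-free survival as endpoints of their own.

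**The concern.** A subject who dies leaves every later by-visit row, and in this disease death often follows from the liver failure that the scores measure. Protocol 1.1 puts short-term mortality in severe alcoholic hepatitis at about 25% to 45%, and 1-month mortality on prednisolone at about 20%. By the later visits a sizeable part of each arm may be absent, and not at random.

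With equal mortality, the selection is similar in both arms and largely cancels. If one arm loses more subjects, and those subjects were on a worse course, its remaining subjects look healthier for that reason alone. The MELD and bilirubin plots could then suggest biological activity in the arm that did worse. The SAP recognises this kind of selection in section 6.5, where it drops the lipid efficacy summaries partly because the sickest subjects would be missing from them.

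**Working it through.** The visible text gives no SD, effect size or expected death rate for these endpoints, so there is no figure of the plan's own to reproduce. Two simple models show the direction and likely size for MELD. In both, the drug has no effect on MELD. The size for CPT, Maddrey DF and bilirubin was not calculated; the mechanism is the same.

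**Inputs.** From the documents: about 50 per arm in the Full Analysis Set (SAP 1.2) and about 20% 1-month mortality on prednisolone (Protocol 1.1). Assumed: 30%, 35% or 40% mortality in the other arm, and the SDs and death models below.

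**Model A (closed form and simulation).** MELD change has mean −2 and SD 6. It correlates at ρ with a latent tendency to die. With mortality p, the survivors' mean change shifts by −SD × ρ × g(p), where g(p) = φ(z_p)/(1 − p).

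- g(0.20) = 0.350, g(0.30) = 0.497, g(0.35) = 0.570, g(0.40) = 0.644.
- Lean towards the higher-mortality arm, against 20%: 0.147, 0.220 and 0.294 × SD × ρ.
- Smallest, 30% versus 20% with ρ = 0.3: 0.147 × 6 × 0.3 = 0.26 points.
- Largest, 40% versus 20% with ρ = 0.7: 0.294 × 6 × 0.7 = 1.23 points.
- At ρ = 0 the lean is zero.

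Simulated differences at 35% versus 20% mortality (higher-mortality arm minus the other; positive is worse), with half of a dying subject's change present in the carried value:

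| ρ | Survivors, mean change | Week 4 (LOCF), mean | Week 4 (LOCF), median | Death ranked worst, median |
|---|---|---|---|---|
| 0.3 | −0.41 | +0.06 | +0.20 | +2.02 |
| 0.5 | −0.66 | +0.01 | +0.22 | +1.60 |
| 0.7 | −0.92 | −0.04 | +0.26 | +1.09 |

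Over 30% to 40% versus 20% and ρ 0.3 to 0.7, the LOCF mean difference runs from −0.04 to +0.10 and the LOCF median difference from +0.13 to +0.33. The worst-rank difference is 0.6 to 3.2 points. At ρ = 0.5 and 35% versus 20%, the LOCF median difference depends on how much of the change is carried. It is 0.0 if all is carried and 0.4 if a quarter is. It is 1.2, against 1.6 for worst rank, if none is.

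**Model B (simulation).** Baseline MELD is 23 (SD 4) and change is −2 (SD 4). Death follows a logistic model with slope 0.25 per MELD point.

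| Mortality | Survivors, mean change | Survivors, median MELD | Death ranked worst, median MELD | Death ranked worst, median change |
|---|---|---|---|---|
| 20% | −2.6 | 19.9 | 21.5 | −1.4 |
| 30% | −2.9 | 19.3 | 22.1 | −0.7 |
| 40% | −3.2 | 18.8 | 23.4 | +0.4 |

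Here death depends on on-study MELD. The survivor columns improve as deaths rise; the worst-rank columns worsen. The lean in mean change is 2.9 − 2.6 = 0.3 points at 30% versus 20%, and 3.2 − 2.6 = 0.6 at 40% versus 20% (0.55 before rounding). The LOCF mean change stays between −2.09 and −1.90 at every mortality level, whether none, half or all of the change is carried.

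If death depends only on baseline MELD, survivors' mean change is −2.0 at all three mortality levels, so change shows no lean. The survivors' absolute MELD still falls, from 20.3 at 20% mortality to 19.7 at 40%.

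**Scale.** With 50 per arm and 35% versus 20% mortality, survivors number 32.5 and 40. The SE of the difference is 6 × √(1/40 + 1/32.5) = 1.4 points. With SD 4 and 40% versus 20% it is 4 × √(1/40 + 1/30) = 1.0.

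**The case against.** The strongest reply is that the plan does not conceal deaths. They are tabulated at Day 28 and Weeks 8, 12 and 24, with Kaplan-Meier curves, and a "Fisher's exact test will be used to explore whether there are differences between treatment groups in percentage of subjects with death by Day 28". Transplant-free survival counts both events. Each continuous summary prints its n (SAP 3), so shrinking rows can be seen. The score changes are descriptive secondary endpoints in a trial whose primary endpoint is safety, and the visible text plans no test on them. The lean is also smaller than its standard error in all but the most extreme assumed settings. SAP 6.5 records that the primary analysis gave no evidence of improved efficacy, so false optimism is now a limited risk.

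Most of this stands, and it limits the consequence. It does not correct the plots. A printed n does not say why subjects are missing, and the death comparison has little power: about 21%, 39% and 59% for 30%, 35% and 40% versus 20% with 50 per arm (normal approximation; lower with Fisher's exact test). A real imbalance could be non-significant while the MELD plot leans the other way.

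A reader might also infer that carrying pre-death values to Week 4 makes the higher-mortality arm look better. The calculations do not support that: the LOCF difference between arms is near zero in the mean, and at or above zero (against that arm) in the median. Nor should those who died simply be deleted from that row. In Model B this would move its mean change from about −2.0 at every mortality level to −2.6, −2.9 and −3.2, which brings the survivor bias into a row that lacked it.

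Finally, a worst-rank median mixes mortality with MELD and is not an estimate of the drug's effect on MELD. That is a reason to present it beside the observed summary, not in its place.

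**Conclusion.** The concern holds for the by-visit rows and plots. They describe subjects alive, untransplanted and sampled, and no worst-outcome or sensitivity summary is planned for them. If mortality differs and deaths concentrate in subjects with a worse course, they lean towards the arm with more deaths by about 0.3 to 1.2 MELD points in mean change. That rests on assumed SDs of 4 to 6, death linked to on-study MELD, and 30% to 40% versus 20% mortality. The lean is zero with equal mortality, and zero for change if only baseline MELD drives death. If the drug truly worsened MELD by 1 point, Model A's survivor difference would show +0.74 to −0.24; the sign reverses only at ρ = 0.7 with 40% versus 20%.

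The Week 4 (LOCF) row creates no advantage. Its fault is that it hides most of the deficit that appears when death is ranked worst, unless the carried values hold almost none of the subjects' change. This is a problem of interpretation, not an error in a formal test. It is worth correcting because the correction is cheap.

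**What to change.** For MELD and total bilirubin:

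- Add a supportive version of the planned median (Q1, Q3) tables and plots in which death or transplant before the visit ranks as the worst value. Where a quartile falls among those subjects, show it as dead/transplanted.
- In that version, use the worst rank at Week 4 in place of a carried-forward value. Leave the existing LOCF row as it is, with a footnote that it includes pre-death and pre-transplant values.

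For all the by-visit summaries in SAP 6.2.8, print the numbers dead and transplanted under each visit, and label the observed-case rows as survivors only.

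The death and transplant dates are already collected for SAP 6.2.1 to 6.2.3, and medians with quartiles are already planned. The cost is a few extra outputs in a less familiar form. Because the primary analysis is already unblinded (SAP 2.3), they should be labelled supportive.
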